Increased knowledge on actual attrition factors and patterns in adolescent populations from mHealth interventions are direly needed. Obtaining a better understanding of how motivational support motivates adolescents to use mHealth applications and why they maintain or lose interest in using them to improve their health is of vital importance. Motivational support in mHealth interventions, defined as strategies to enhance motivation and counter attrition to overcome behavior change barriers, often include goal-setting, feedback, social support and rewards (36-37). Systematic reviews examining possible drivers behind usage point to group and task customization, localization, functional user support, gamification of health tasks and immediate visual but simplified feedback on user action while while gender-related motivational support features could be contributing factors [36-38]. Timing of tailored motivational support, through just-in-time adaptive interventions (JITAI), should be considered as well when implementing adolescent mHealth interventions since time-based individualization could counter high attritions rates [35, 39]. Given the magnitude of reported health problems among adolescents and lack of cost-effective health behaviour interventions specifically developed for adolescent populations, the need for better understanding of attrition reasons in adolescent mHealth interventions is massive. The purpose of this study was firstly to seek richer understanding of continuous attrition rates from a mHealth intervention in an adolescent population and what effects motivational support has on attrition rates. Secondly, the aim was to examine effectiveness of the intervention with the aim to increase daily mental, nutritional and physical health behaviour.

Methods

Participants

Participants are adolescents, age 13 to 16 years old, attending one of three public schools for children and adolescents in the greater capital area of Iceland. All children attending the oldest 3 classes, called 8th to 10th classes, in three participating public elementary schools in

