Iceland are eligible participants (n=661, m:f ratio=313:348). All children in public schools in the municipality are equipped with an iPad from 10 years of age. Exclusion criteria are diagnosis of severe disorder of intellectual development and/or physical-, developmental- and mental illness significantly restricting ability to use mobile apps. Research specifications and introduction to the application will be sent via email to parents and legal caretakers of all eligible participants through school officials along with confirmative survey link. If the link is answered, it yields confirmation for informed consent. Adolescents with informed consent from parents/legal caretakers will then invited to take part in the study through confirmative survey link. The study has been approved by the National Bioethics Committee (license number: VSNb2015060065/03-01).

Measurements

Original primary outcome measure will be app acceptability and functionality, measured with *Systematic Usability Scale* (SUS), a widely used and relatively well studied 10-item questionnaire on app usability where scores range from 0-100 and total score over 70 yielding satisfactory usability and user acceptance [40, 41]. Further primary measures were amount, frequency and time of daily physical activity measured through in-app activity, self-reported stress levels, quality of sleep and energy levels, measured through levels of the health app usage and completion of in-app health tasks.

Secondary outcome measures include standardized body mass index (*BMI-SDS*) based on BMI index reference values for Swedish children and adjusted for age and sex. Participants are weighed in kilograms in light clothing without shoes using a digital scale (Marel type C2; Marel, Reykjavik, Iceland). Height is measured in centimetres using a wall-mounted stadiometer (Seca stadiometer; Seca, Hamburg, Germany).

Anxiety and depressive symptoms will be assessed using the *Revised Children's Anxiety and Depression Scale* (RCADS), a self-report assessment tool for children and youth. The scale is a four point Likert scale, spans 47 questions and is divided into 6 subscales; separation anxiety symptoms, general anxiety symptoms, obsessive-compulsion symptoms, social anxiety symptoms, panic symptoms, depression symptoms. A *T*-score over 65 marks a clinical cut-off point. The inventory's psychometrics have been studied with acceptable findings in both US and Icelandic paediatric populations [42, 43].

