
Figure 1. Overview of app functions & categories

[figure not shown]

Procedure

The study is a randomized controlled study. Cluster randomization is used to distinguish three participating schools into control, treatment-as-usual (TAU) and intervention groups. Measures will be obtained at baseline and 42 days later. Participants in both the TAU group and the intervention group receive an approximately 10 minutes long introduction regarding the study specifications and the application. The control group receives no further contact, access to the application or information until study-end questionnaire measures. Participants in the intervention group are randomly assigned to teams consisting of 8 individuals that collectively and individually compete in point collection through completion of in-app health tasks. Participation in the TAU group and intervention group is defined as downloading the Sidekick app and completing at least 3 health exercises within it. Time of exercise is defined as the timestamp on completion of exercise within any of the three types of exercise categories (physical activity, nutrition and mental health) of the app. Exercise frequency refers to how often a given exercise was completed by a participant. Time of attrition was defined as the time stamp of last completing health exercise within the Sidekick throughout intervention period. The procedural difference between TAU group and intervention group evolves around motivational support. The intervention group receives weekly motivational support in form of individual and group feedback on usage, participation in friendly health task competitions and weekly altruistic rewards for usage. Participants in TAU group use the

application individually throughout trial period without any motivational support. A flow chart of participation is displayed in figure 2.

Figure 2. Participant flow chart

Statistical analysis

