Descriptive characteristics of participants along with attrition reason are reported. Pearson's correlation coefficient, independent samples *t*-tests, repeated measures ANOVAs with adjusted alpha levels, and χ^2 tests will be used to measure mean differences from baseline to trial's end within and between research groups on primary and secondary outcome measures. Kaplan-Meier survival analysis plots and logrank tests are deployed to assess time of attrition and possible significant differences between and within research groups [50, 51]. Trial beginning is defined as time of first in-app health exercise completion and the trial period was six weeks, or 42 days, from that moment. Attrition, or the event, is defined as the time of participants' last completed health exercise in SidekickHealth. Participants' cases will be evaluated as censored when the application was still being used 42 days after study start. Cox proportional hazard regression models with interacting covariables using research groups as clusters was used to examine attrition prediction based on usage of in-app health exercises between time, type and frequency of exercises as well as sociodemographic variables (age,

gender) [52]. Significance will be defined at $p < .05$. Data was analysed using IBM SPSS Statistics, Release Version 29 (SPSS, Inc., 2009, Chicago, IL, USA, <http://www.spss.com>).

References

1. Smith, A. (2015, April 1). *U.S. Smartphone Use in 2015*. Pew Research Center. <https://www.pewresearch.org/internet/2015/04/01/us-smartphone-use-in-2015/>
2. Silver, L. (2019, February 5). *Smartphone Ownership Is Growing Rapidly Around the World, but Not Always Equally*. Pew Research Center <https://www.pewresearch.org/global/2019/02/05/smartphone-ownership-is-growing-rapidly-around-the-world-but-not-always-equally/>
3. Anderson, M. & Jiang, J. (2018, May 31). *Teens, Social Media and Technology 2018*. Pew Research Center. <https://www.pewresearch.org/internet/2018/05/31/teens-social-media-technology-2018/>
4. Jones, E. A. K., Mitra, A. K. & Bhuiyan, A. R. (2021). Impact of COVID-19 on Mental Health in Adolescents: A Systematic Review. *The International Journal of Environmental Research and Public*, 18(5). <https://doi.org/10.3390/ijerph18052470>
5. Körmendi, A. (2016). Smartphone usage among adolescents. *Psychiatria Hungarica: A Magyar Pszichiátriai Társaság Tudományos Folyóirata*, 30(3), 297-302.

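### Participation in the two app schools depends on app use after allocation, but control has no usage condition, so on the most direct reading the effectiveness comparison sets engaged pupils against pupils not selected on engagement

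*Combined protocol and SAP*

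**What the plan says.** All references are to the combined protocol and SAP.

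- **Allocation** (Methods, Procedure): "Cluster randomization is used to distinguish three participating schools into control, treatment-as-usual (TAU) and intervention groups". There is one school per arm.
- **Entry, all schools** (Methods, Participants): the parent answers a survey link, and "If the link is answered, it yields confirmation for informed consent". The pupil follows: "Adolescents with informed consent from parents/legal caretakers will then invited to take part in the study through confirmative survey link". Neither step asks for any app use.
- **Further condition, two schools only** (Procedure): "Participation in the TAU group and intervention group is defined as downloading the Sidekick app and completing at least 3 health exercises within it".
- **Control** (Procedure): "The control group receives no further contact, access to the application or information until study-end questionnaire measures". No definition of participation is given for this school.
- **Timing**: Procedure places the measures at baseline and 42 days later. Statistical analysis starts the trial at the first exercise completed in the app and runs the six weeks from there.
- **Comparison** (Statistical analysis): mean differences from baseline to the end of the trial are tested "within and between research groups on primary and secondary outcome measures". No intention-to-treat or all-consenters set is named, and nothing says how consenting pupils with fewer than 3 exercises are handled.
- **Aim** (end of the introduction): "Secondly, the aim was to examine effectiveness of the intervention with the aim to increase daily mental, nutritional and physical health behaviour".

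**The concern.** Randomisation protects a comparison only if membership of each analysed group is settled by allocation and by things fixed before it. Downloading the app and completing 3 exercises happens after allocation, can happen in only two of the three schools, and is itself health behaviour.

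The plan's own introduction makes selection plausible. It says attrition in adolescent mobile interventions is generally high, and that inactivity and poor diet are often linked with emotional problems. Pupils who complete health exercises may therefore differ from those who do not on what RCADS, GSE, BEARS and BMI-SDS measure.

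The second aim is at stake. Control is the only school that shows what happens without the app. If the app schools contribute only engaged pupils, the difference from control can mix any effect of the app with the course those pupils would have followed anyway.

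The point is confined to outcomes that control can supply. Usability and in-app activity do not exist without the app, and the TAU-versus-intervention attrition curves are a separate matter.

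**Working it through.** The plan gives no sample size, effect size, SD, consent rate or share of pupils reaching 3 exercises, so it has no figure of its own to reproduce. The one related count agrees: 313 + 348 = 661 eligible pupils, or 661/3 = 220 per school on average.

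**Step 1: who is in each group.**

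| Condition | App schools | Control | Source |
|---|---|---|---|
| Parental consent by link | yes | yes | Participants |
| Pupil invited by link | yes | yes | Participants |
| Download plus at least 3 exercises | yes | cannot apply | Procedure |

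**Step 2: does the rule reach the questionnaire outcomes?** Statistical analysis does not say so outright. But it names no wider set, and it starts the trial at the first completed exercise. Under that definition a consenting app-school pupil who never does an exercise has no trial start and no day 42. Applying the 3-exercise definition to these outcomes is therefore the most direct reading, though still an inference.

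**Step 3: effect on day-42 levels.** Let f be the share of consenters failing the rule and d the passer-minus-failer difference without any app effect. The consenters' mean is the passers' mean minus f × d, so keeping passers alone shifts the mean by f × d. Both inputs are assumptions: f = 0.20 to 0.50, d = 0.2 to 0.4 SD.

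- Low: 0.20 × 0.2 = 0.04 SD.
- High: 0.50 × 0.4 = 0.20 SD.

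**Step 4: effect on change, which is what the plan compares.** If d is the same at baseline and day 42, it cancels within pupils and the bias in change is zero. Bias in change needs passers to follow a different course without the app. To illustrate, let s be the share of consenters passing and rho the correlation of underlying engagement with change (both assumed; the sign is arbitrary). With no true effect:

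bias = rho × φ(z) / s, where z is the standard normal quantile at 1 − s and φ is the normal density.

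For s = 0.6 and rho = 0.2: z = −0.253, φ = 0.386, bias = 0.2 × 0.386 / 0.6 = 0.129 SD.

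With n consenters per school, SE = √(1/n + 1/(s × n)). For n = 200: √(1/200 + 1/120) = 0.1155, and 0.1288 / 0.1155 = 1.115. The false-positive rate at two-sided 0.05 (the plan does not state sidedness) is Φ(1.115 − 1.96) + Φ(−1.115 − 1.96) = 0.20.

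| s | rho | Bias (SD) | False positives, n = 100 | False positives, n = 200 |
|---|---|---|---|---|
| 0.9 | 0.1 | 0.02 | 0.052 | 0.054 |
| 0.8 | 0.2 | 0.07 | 0.075 | 0.101 |
| 0.6 | 0.2 | 0.13 | 0.124 | 0.200 |
| 0.4 | 0.3 | 0.29 | 0.341 | 0.591 |

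These rates ignore clustering by school.

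**Step 5: check by simulation and effect of the remedy.** With 5000 simulated trials per case and n = 200, users versus control gave false-positive rates of 0.202 (s = 0.6, rho = 0.2), 0.096 (0.8, 0.2) and 0.595 (0.4, 0.3), in line with the formula. Analysing all consenters gave 0.045, 0.058 and 0.050. In this model the selection bias is then zero, provided day-42 data are obtained from everyone.

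**The case against.** The strongest reply is that the plan never says the questionnaire and BMI outcomes are restricted to pupils meeting the 3-exercise rule. The rule sits directly before definitions of exercise time, exercise frequency and attrition, so it could be meant for the usage analysis alone. The word participants is also used more widely: the Participants section defines them by age and school, and Procedure gives participants in both app schools a 10-minute introduction that presumably precedes any exercise. This stands as a limit on certainty. It does not remove the problem, because no other set is named and the text would need changing under either intention.

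A second reply concerns change scores: a stable difference between engaged and other pupils cancels. This is correct, and it means the 0.04 to 0.20 SD of Step 3 applies to day-42 levels only. A differing course over 42 days is plausible but not shown.

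Third, only secondary outcomes are touched, and for control Procedure mentions only questionnaires at study end, so BMI-SDS there is uncertain. Both limits stand. The participant flow chart is also not shown in the text available for review; it may count or define participants by arm.

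Two stronger readings are tempting. A reader might infer that control pupils enter by consent alone and that every consenter counts. The documents do not say so: pupils are also invited by link and must complete questionnaires to contribute data. All that is supported is that control has no usage condition. A reader might also infer that the exclusion for conditions such as "mental illness significantly restricting ability to use mobile apps" works unevenly across schools. On paper it applies to all three alike, and nothing shows that it would not be applied in control.

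**Conclusion.** The concern holds in this form. The plan makes participation in two of three arms depend on behaviour after allocation, the third arm has no counterpart, and the between-group comparison names no set that would undo this. That the rule governs RCADS, GSE, BEARS and BMI-SDS is the most direct reading, supported by the definition of trial start, but it is not stated.

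The comparison with control can be biased if engaged pupils would change differently over 42 days without the app. Neither size nor direction follows from the documents. Under the assumptions shown, the effect runs from negligible (0.02 SD, false-positive rate about 0.05) to serious (0.29 SD, 0.59 with 200 consenters per school). A reader might infer that the effectiveness result is certainly biased, or biased in the app's favour; the documents support neither.

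Having one school per arm is a separate weakness, which correcting the participant definition does not cure.

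**What to change.** For RCADS, GSE, BEARS and BMI-SDS:

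- In Procedure, define a participant identically in all three schools: parental consent, pupil agreement and a completed baseline.
- In Statistical analysis, state that these outcomes are analysed by allocated school whatever the app use, with day 42 counted from baseline in every school.
- Seek day-42 measures from pupils who never reach 3 exercises.
- State whether BMI-SDS is measured in control.

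Keep the 3-exercise rule for the app-usage and attrition analyses only. Their clock starts at the first exercise and need not change.

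Some of the plan is in the past tense, so data collection may be over. In that case, analyse all pupils with a baseline and available day-42 data, and report by arm how many pupils the 3-exercise rule removes. This is weaker: if non-users were not followed up, some of the selection remains as missing data and should be acknowledged.

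The cost is a few sentences in two sections and some extra day-42 forms from pupils in schools already taking part. The app-versus-control effect may look smaller because non-users are included.

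### The app-logged count used for daily physical activity has no time-in-use denominator, so in TAU versus intervention a retention effect alone can look like more activity

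*Combined protocol and SAP*

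**What the plan says.** Under Measurements, the plan lists physical activity among its primary measures and takes it from the app: "Further primary measures were amount, frequency and time of daily physical activity measured through in-app activity". The same sentence ends by naming the instrument: "measured through levels of the health app usage and completion of in-app health tasks". No other source of physical activity data is given.

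Under Procedure, frequency is defined without a denominator: "Exercise frequency refers to how often a given exercise was completed by a participant". The end of logging is itself an outcome: "Time of attrition was defined as the time stamp of last completing health exercise within the Sidekick throughout intervention period". A pupil in either app arm counts as a participant after "downloading the Sidekick app and completing at least 3 health exercises within it". The arms differ in motivational support, which includes "weekly altruistic rewards for usage"; the TAU arm uses the app without it.

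Under Statistical analysis, the clock starts at the first in-app exercise and "the trial period was six weeks, or 42 days, from that moment". Correlations, t-tests, repeated measures ANOVAs and chi-square tests "will be used to measure mean differences from baseline to trial's end within and between research groups". No offset, rate per day in use or rule for days after the last logged exercise is given. Time in use is analysed only as a separate attrition outcome, by Kaplan-Meier, logrank and Cox methods.

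The introduction closes with two aims: first, attrition and the effect of motivational support on it; second, whether the intervention increases daily health behaviour.

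**The concern.** Physical activity is visible only while a pupil logs it. A pupil who stops logging on day 10 may be as active as before but adds nothing for the remaining 32 days. Dividing the count by a fixed 42 days does not help, because it rescales every pupil by the same constant.

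This would matter little if both app arms logged for equally long. The trial is built to find out whether they do not: the intervention arm is rewarded for usage and the TAU arm is not. If support only delays attrition, the first aim succeeds, and the undivided count carries that success over to the second aim as an apparent rise in daily physical activity. One finding would then be reported as two.

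The point is confined to TAU versus intervention, where both arms have app data. It does not depend on the absence of app data in the control arm, or on how frequency is used as a predictor in the Cox models.

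**Working it through.** The plan states no sample size, daily rate or expected time in use, so there is no figure of its own to reproduce.

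**1. How much the definition leaves open.** Inputs from the plan: a minimum of 3 exercises (Procedure) and a 42-day period (Statistical analysis). Take a pupil who completes 3 exercises, all on day 1:
- over the trial period: 3/42 = 0.07 per day;
- over the one day in use: 3/1 = 3.0 per day.

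The two readings of a daily figure differ 42-fold.

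**2. Count ratio when true activity is equal.** Assumed: exponential attrition and the same daily rate while in use in both arms. With median use m and k = ln 2/m, mean days in use within 42 days are (1 − exp(−42k))/k.
- m = 14: k = 0.0495, exp(−42k) = 1/8, mean = 0.875/0.0495 = 17.7 days (42% of 42).
- m = 21: k = 0.0330, exp(−42k) = 1/4, mean = 0.75/0.0330 = 22.7 days (54% of 42).

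The expected count is rate × mean days in use. At an assumed 0.6 completions per day in use, this is 0.6 × 17.7 = 10.6 versus 0.6 × 22.7 = 13.6. The rate cancels in the ratio: 22.7/17.7 ≈ 1.29.

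| Median days in use, TAU v intervention | Mean days in use | Count ratio |
|---|---|---|
| 14 v 14 | 17.7 v 17.7 | 1.00 |
| 21 v 28 | 22.7 v 26.1 | 1.15 |
| 14 v 17.5 | 17.7 v 20.5 | 1.16 |
| 14 v 21 | 17.7 v 22.7 | 1.29 |
| 7 v 10.5 | 9.9 v 14.2 | 1.43 |
| 14 v 28 | 17.7 v 26.1 | 1.48 |

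**3. The participation rule.** Step 2 includes very short users, whom the three-exercise rule would remove. Simulation of 14 v 21 days used 0.6 completions per day in use, between-pupil gamma variation with shape 2, a two-sided Welch t-test on counts at 0.05, and no allowance for clustering by school.

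| | Excess count | Rejection, 60 per arm | 100 per arm | 200 per arm |
|---|---|---|---|---|
| Rule not applied | about 29% | about 22% | about 32% | about 55% |
| Rule met by these completions | about 18% | about 17% | about 24% | about 44% |

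If pupils meet the rule through nutrition or mental health exercises, the reduction is smaller. An average school has 661/3 ≈ 220 eligible pupils, so 200 per arm would need about 90% to enrol and qualify. The smaller sizes are more realistic.

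**4. Dividing by days in use.** A second simulation assumed 1 completion per day in use, a between-pupil coefficient of variation of 0.5 and no participation rule. The count divided by days in use rejected in 4% to 6% of trials in every scenario. The undivided count rejected in 24% (50 per arm) and 45% (100 per arm) for 14 v 21 days, and in about 5% for 14 v 14 days.

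**The case against.** The strongest reply is that the plan never commits to the analysis criticised. A reader might infer that every day after the last log is scored as zero activity, but no such rule is written. The word daily could point to a rate, and the analysis sentence speaks of change from baseline to trial's end, not of whole-period totals. This stands as far as it goes: the zero follows only from using an undivided count, or a count over 42 days. But only division by days in use would avoid the problem, and the plan states no such denominator.

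Second, the definition of frequency may be meant mainly for the Cox predictors, which include time, type and frequency of exercises. That link is clear, and the link to the activity outcome is partly inferred. Yet it is the only definition of frequency in the plan, and the primary measure names frequency of in-app activity.

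Third, a zero is correct for exercises completed in the app. Keeping every participant's full 42 days preserves the comparison by allocated arm, and longer task completion may be a real benefit. This stands fully. The fault lies in reading logged completions as physical activity.

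Fourth, a reader might infer that only amount per logged day can show increased activity. That does not follow. If support moved pupils from two active days a week to five at the same amount per active day, that ratio would be 1.00 although activity had risen 2.5-fold (5/2). It would also discard frequency, which the plan names as a primary measure.

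**Conclusion.** The concern holds as a confounding of retention with activity in the TAU versus intervention comparison. It is more than missing detail: the app is the only source, the count has no denominator, and the arms differ in rewards for the behaviour that produces the data. As written, the plan allows a success on attrition alone to be reported as increased daily physical activity.

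The size is illustrative. For assumed medians of 14 versus 21 days, the spurious excess is about 29%, or about 18% with the participation rule met by these completions. In the latter case false rejection is about 17%, 24% and 44% at 60, 100 and 200 per arm, against a nominal 5%. These figures rest on exponential attrition, an equal daily rate while in use and independent pupils. If the arms log for equally long, there is no bias. The documents do not support reading any of these figures as the bias to be expected in this trial. This should be corrected, but it does not make the app-logged total invalid as a measure of usage.

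**What to change.** - **Measurements:** label the 42-day total as app-logged activity (usage), and keep it as the comparison of all participants by allocated arm.
- **Procedure:** state the denominator whenever frequency is used as a daily measure, and say how days after the last logged exercise are treated.
- **Statistical analysis:** beside the total, report physical activity per day in use, with days in use running from first to last logged exercise. Show its two parts, since activity per day in use = (active days ÷ days in use) × amount per active day. Describe it as conditional on continued use.
- **Conclusions:** state that the 42-day total alone will not support a claim that daily physical activity increased. Do not make amount per active day the sole test of that claim.

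The cost is wording in three sections and some further analysis of timestamps the plan already collects; no new data are needed. The downside is that activity per day in use conditions on behaviour after allocation. Support that retains less active pupils would dilute it, and it is unstable for very short users. It is supportive evidence, not a full causal cure.

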General Self Efficacy Scale (GSE), a 10 item self-report questionnaire with ranging total scores from 10 to 40, is used to measure self-efficacy levels where higher score yielding increases self-efficacy [44]. Acceptable psychometric properties for the questionnaire have been obtained and it is used globally in youth populations [45].

[figure not shown]
BEARS sleep screening algorithm will be used to evaluate participant's sleep problems. It is a sleep screening instrument for children from 2 to 18 years old, divided into 5 sleep domains; bedtime problems, excessive daytime sleepiness, awakenings during night, regularity and

duration of sleep and snoring [46]. The algorithm's psychometrics have been studied with acceptable findings in paediatric populations [47].

mHealth application

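### The pooled list of tests is not assigned to contrasts, and chi-square, the only method named for categorical outcomes, is not valid for within-arm change and ignores baseline between arms

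*Combined protocol and SAP*

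**What the plan says.** The Procedure section of the combined protocol and SAP fixes two measurement occasions: "Measures will be obtained at baseline and 42 days later". Each pupil therefore contributes a pair of values. The same section allocates three schools to three arms, one school to each.

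The Statistical analysis section names Pearson's correlation, "independent samples *t*-tests", "repeated measures ANOVAs with adjusted alpha levels" and chi-square tests in one list. It gives the whole list one purpose: these "tests will be used to measure mean differences from baseline to" the end of the trial, "within and between research groups on primary and secondary outcome measures". It does not say which test serves the within-group contrast, which serves the between-group contrast, or which outcome each applies to. No paired method for categorical data is named.

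Two instruments in the Measurements section could yield categorical outcomes. BEARS is "divided into 5 sleep domains; bedtime problems, excessive daytime sleepiness" and three others. RCADS is described with a clinical cut-off at a T-score of 65. The section does not say whether BEARS is analysed as yes/no domains or as a score, or whether RCADS status above the cut-off is an outcome at all.

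**The concern.** The independent t-test and the usual chi-square test assume that the observations compared are independent. A baseline value and a day-42 value from the same pupil are not. The list covers within-group change, so an analyst could apply either test to that change and still comply with the plan.

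For continuous scores a suitable method is in the list. For categorical outcomes none is, because chi-square stands alone. An analyst would have to use a test that does not fit within-arm change, or choose another one after seeing the data.

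Between arms, a chi-square test on day-42 status makes no use of baseline status, although it is collected. With one school per arm, baseline status may differ between arms, and a difference present at the start would carry into the day-42 comparison.

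The plan also sets within-arm and between-arm tests side by side without saying which of them decides effectiveness.

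**Working it through.** The documents give no sample size, effect size, standard deviation, prevalence or baseline-to-end correlation, so there is no planned figure to reproduce. All numerical inputs below are assumptions for illustration, except the significance level of 0.05 (Statistical analysis), which is taken as two-sided because sidedness is not stated. The arm size of 100 is assumed; 661 pupils are eligible across the three schools (Participants).

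**Continuous scores, within one arm**

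- Method already listed: with two time points, repeated measures ANOVA gives F = t² of the paired t-test. A numerical check gave 0.00756 for both.
- If the independent t-test were used instead, its standard error would be too large by 1/√(1−ρ): 1.20 at ρ = 0.3, 1.41 at 0.5 and 1.83 at 0.7. The true size of a nominal 0.05 test would be 0.019, 0.0056 and 0.0004. The error is conservative.
- Power at ρ = 0.6, n = 100 and a change of 0.2 SD:
  - The independent test rejects when the difference exceeds 1.96 × √(2/100) = 0.277.
  - The true standard error of the difference is √(2 × 0.4/100) = 0.0894.
  - Independent test: Φ((0.200 − 0.277)/0.0894) = Φ(−0.86), about 19%.
  - Paired test: Φ(0.200/0.0894 − 1.96) = Φ(0.28), about 61%.

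**Yes/no outcomes, within one arm**

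Simulation with 20,000 runs per cell and n = 100. The size columns assume 30% prevalence at both times; the power columns assume a fall from 30% to 20%. Correlation is that between baseline and end status.

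| Correlation | Size, unpaired chi-square | Size, McNemar | Rejections with no change, chi-square on crosstab | Power, unpaired chi-square | Power, McNemar |
|---|---|---|---|---|---|
| 0.3 | 0.020 | 0.053 | 0.842 | 0.348 | 0.506 |
| 0.5 | 0.006 | 0.052 | 0.998 | 0.321 | 0.649 |
| 0.7 | 0.000 | 0.042 | 1.000 | 0.273 | 0.877 |

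The two ways of using chi-square fail differently. Treating baseline and end as separate samples is conservative and loses power. Crossing baseline with end status tests whether the two are associated, which they almost always are. A significant result there says nothing about change.

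**Yes/no outcomes, between two arms**

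Suppose one school stands at 30% and another at 20% at both times, with 100 pupils each and no effect of the app.

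- Chi-square on day-42 status rejects when the difference exceeds 1.96 × √(0.25 × 0.75 × 2/100) = 0.120.
- The true standard error is √(0.3 × 0.7/100 + 0.2 × 0.8/100) = 0.0608.
- The chance of rejection is Φ((0.100 − 0.120)/0.0608) = Φ(−0.33), about 37%.
- With correlation 0.5, P(yes at end | yes at baseline) = p + 0.5(1 − p), which is 65% and 60% in the two schools. P(yes at end | no at baseline) = 0.5p, which is 15% and 10%. Conditioning on baseline status cuts the spurious gap from 10 points to 5. It does not remove it.

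**The case against.** The strongest reply is that the sentence is a loose list and should be read sensibly. Repeated measures ANOVA is the natural partner of the within-group contrast; independent t-tests and chi-square are natural partners of the between-group contrast. Read literally, the sentence would also make Pearson's correlation a test of mean difference. Two-sample tests have an evident use too, since app-usage outcomes exist only in the two arms with the app. This stands. A reader might infer that the plan prescribes independent t-tests for within-arm change, so that the standard errors for RCADS, GSE or BMI-SDS scores are wrong. The documents do not support that: they assign no test to that contrast, and a valid one is in the list.

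A second reply is that the categorical problem rests on outcomes the documents never define as categorical. That also stands, and the conclusion is conditional for this reason. It does not close the point: the plan applies chi-square to its outcome measures, so some categorical analysis is intended, and no paired alternative is offered.

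A third reply is that an unadjusted between-arm chi-square test is not invalid merely because it omits baseline. In a trial that randomised many units this would be mainly a loss of precision. With one school per arm, chance balance cannot be relied on, so the omission matters more here.

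Finally, a reader might infer that effectiveness will be claimed from significance in one arm and its absence in another. The documents do not say so, and they do plan between-group tests. They simply do not rule it out.

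**Conclusion.** The point holds in a limited form. For continuous scores the defect is one of assignment: a method that handles pairing is listed, and an independent t-test used within an arm would lose power (about 19% against 61% at ρ = 0.6, n = 100 and 0.2 SD) without adding false positives, given positive correlation.

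For any outcome analysed as categories, the plan names no valid test of within-arm change, and its only between-arm test leaves baseline status unused. The within-arm loss is material over the assumed range. The crosstab use is the more serious error, because it would almost always be significant without any change.

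These sizes rest on assumed prevalence, correlation, effect and arm size, and on BEARS or RCADS being analysed as yes/no. Within-arm change is not the randomised comparison, so its bearing on the trial's main conclusions is limited.

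**What to change.** In the Statistical analysis section, give each test its contrast and outcome:

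- Within-arm change in continuous scores: repeated measures ANOVA. Confine the independent t-test to between-arm contrasts.
- Within-arm change in yes/no outcomes: McNemar's test.
- Between-arm comparison of yes/no outcomes: logistic regression of day-42 status on arm and baseline status.
- State how BEARS is scored for analysis, and whether RCADS above the cut-off is an outcome.
- State that within-arm results are descriptive and that effectiveness is judged on between-arm estimates.

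The cost is a few sentences of SAP text and a little more analysis work on data already planned for collection. The change does not solve the separate problem that each arm is a single school. As the between-arm illustration shows, baseline adjustment removes only part of a difference between schools, and the write-up should say so.
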